CONFIDENTIAL: PROPRIETARY INFORMATION

Therapeutic monoclonal antibody combinations

In regions in which these are available, they will either be administered at the investigative site or patients will be informed as to where they can receive the antibodies. Use of the antibodies will be discussed with each patient in regions in which they are available. It is the patient's decision whether or not to receive the antibody combination.

Other Tests and Procedures

Patients will complete a smartphone-based diary at baseline and daily from day 2 (the second treatment day) through day 28 and days 1, 3 and 5 each subsequent week during the study. This will collect symptom information, adverse events, and study and concomitant medication administration. A patient who is unable to enter the diary data independently at baseline should not be enrolled in this study. If, however, the patient becomes physically unable to complete the diary during the course of the study, he or she may dictate responses to a caregiver or other companion; that the caregiver is completing the diary should be noted. If the patient is unable to respond to the questions during the course of the study, that should be so noted. A caregiver or companion should *not* complete the diary using assumed responses. The patient will be deemed not to have recovered on any day when he or she is unable to provide responses to the diary questions. If difficulties in use of the smartphone-based diary system occur, paper forms may be substituted for individual patients or in regions in which the smartphone-based system does not function properly.

If the baseline diary is completed on treatment day 1, rather than prior to treatment day 1, the patient should not complete the diary again that evening. The information to be collected is shown in Appendix 2.

At the baseline visit, patients will receive a kit which contains devices for remote patient monitoring. The kit includes:

- Electronic thermometer
- Pulse oximeter
- 6-lead ECG

The ECG device may be kept by the site personnel or by the patient, depending on convenience and logistics at each site.

All devices are FDA-cleared (i.e., approved via 510K pathway).

Patients and caregivers will be trained on use of all devices at their baseline visit and will be given additional documentation at the time of the baseline visit.

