7.1 Sample Size Considerations

Part A

In the first part of this study, two different dose levels of upamostat will be tested; randomization will be 1:1:1 to the two upamostat dose levels and placebo.

The objective of this part is to evaluate the tolerability of two dosing levels of upamostat in order to select the dose level that will be evaluated in the confirmatory Part B of the study.

The sample size for part A, consisting of 20 subjects per each arm (placebo, upamostat 200 mg qd, upamostat 400 mg qd) was not chosen for statistical power consideration, as there are no formal statistical inferences planned. The size of this part is judged adequate for the tolerability assessment.

Part B

After accrual to the first part of the study is completed and a determination as to which active arm to continue into the next part of the study is made, accrual will continue at a 3:2 ratio, active:placebo. A minimum total of 250 patients will be accrued to part B, 150 to the active arm using the regimen selected in part A of the study and 100 to placebo.

The sample size currently shown for part B was determined based on the primary endpoint, time to sustained recovery from COVID-19 illness, as defined in the primary objective. It was calculated that in order to detect a hazard ratio for sustained recovery=1.5 comparing the active group to placebo group with 3:2 allocation ratio, a total of 201 recovery events are required, to provide 80% power using a log-rank test at a two-sided significance level of 0.05. Assuming 80% sustained recovery rate in the control arm by end of follow-up (assumed equal follow-up of 57 days for all enrolled patients), it was calculated that in order to achieve the required number of events, the minimum number of patients enrolled will be 250 in total. As this study is defined as an operationally seamless phase 2/3 study, subjects from the part A of the study will not be combined with those in part B for the efficacy analysis. Therefore the target enrollment for part B is the total number of required subjects, namely 250 subjects in total, 150 and 100 for the active and placebo groups, respectively.

The target number of events for this event-based part B portion is 201, taking into account a non-binding futility analysis that will be performed when 50% of the information (primary events) have been realized.

Sample size re-assessment

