7.4 Efficacy Analyses

7.4.1 Analysis of the primary efficacy endpoints

The primary endpoint of the study is time to sustained recovery from COVID-19 illness, as defined in section 2 of the protocol. The first secondary endpoint, incidence of hospitalization or death, will primarily be assessed in the high risk or very high risk population.

Time to sustained recovery is the number of days from first dose of study medication until the day on which patient is recovered and remains recovered for at least 14 days or until end of study, whichever comes first. The definition of "sustained" may be modified, as noted above, at the end of part A. First date of recovery will be defined as the **latest** time among the events below:

- 1) Start date of the period during which the patient is afebrile for at least 48 hours without use of antipyretics;
- 2) First date when all symptoms have resolved or returned to pre-illness levels (e.g., if patient had baseline respiratory compromise), except for
 - a. fatigue, anosmia, ageusia or dysgeusia, which may be persistent at levels similar to the acute illness, or
 - b. dyspnea, cough or chest pain, which, if persistent, must be at least one grade lower than baseline and no worse than grade 1 (mild).

Time will include the first day of study medication and the day on which patient is declared to have recovered.

Patients who have reached day 57 from the start of treatment but have not recovered will be censored at day 57. In addition, several situations override the above definition of recovery:

 Patients lost to follow-up during treatment or follow-up (before recovering) will be censored at day 57.

- Patients who recover per the definition above but are subsequently hospitalized for any reason and are in hospital at day 57 will be censored at day 57.
- Patients who die before recovery will be censored at day 57, the end of follow-up, reflecting the most unfavorable possible outcome for this endpoint.

Calculation of time to sustained recovery requires completion of the symptom diary. If a patient is hospitalized, he or she will be considered as not recovered on those days, regardless of the reason for hospitalization.

Supportive analysis will be performed to include recovery from viral shedding in the definition of recovered event. In this analysis time to recovery will be the latest between the two events above and time of first negative nose viral swab.

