The comparison of the time to sustained recovery between active and placebo groups will be performed using stratified log-rank test, at 5% significance level. The stratification factors used for randomization will be used. Kaplan-Meier plots of time to sustained recovery will be provided along with median estimates and hazard ratio (HR) will be estimated along with 95% confidence interval using stratified Cox regression model. Estimates of cumulative incidence of sustained recovery at certain time points (for example days 15, 29, 43 or 57) for each group, along with 95% confidence interval will be tabulated.

More details on statistical analyses of the primary endpoint and sensitivity analyses will be provided in the SAP. These will address the following aspects:

- Using the PP population and ITT population
- To account for the possibility of errors in values of stratification factors used for randomization, the primary analysis will supportively be repeated using the correct values.
- Comparison between the treatment and control groups when controlling for
 possible imbalance in important baseline factors will be analysed by evaluating
 the HR obtained from estimating a multiple proportional hazards Cox regression
 model.

Subgroups to be analyzed, such as various risk categories, will be enumerated in the SAP. Handling of missing data will be described in the SAP.

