4.2 Covariate Adjustment

In part B only, primary analyses will adjust for stratification factors used in the randomization, but strata

may be combined if they are too small. Additional covariate adjustments may be done in sensitivity and

exploratory analyses. The stratification factors used in the randomization or covariates of interest will be

investigated via the subgroup analysis as detailed below.

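### The part B primary analysis leaves out baseline symptom severity, a likely predictor of recovery that every patient records: a missed efficiency, not an error in the stated power

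*Protocol*

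**What the plan says.** Protocol 7.4.1 fixes the primary test: "The comparison of the time to sustained recovery between active and placebo groups will be performed using stratified log-rank test, at 5% significance level". The strata are the randomization factors, and the hazard ratio is estimated from a Cox model stratified in the same way. Protocol 4.1 lists the part B factors as concerning conditions (none versus at least one), planned antibody treatment, region and vaccination status; it also mentions age. None is a measure of symptoms.

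Other baseline variables appear in two places. Protocol 7.4.1 promises a supportive multiple Cox model to deal with chance imbalance, but names no covariates. SAP 4.2 says that "Additional covariate adjustments may be done in sensitivity and" exploratory analyses.

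Baseline severity is available for everyone. Protocol 5.2 says: "Patients will complete a smartphone-based diary at baseline and daily from day 2". Inclusion criterion 3 also depends on that first questionnaire. Protocol 7.4.1 defines recovery from the same items. Most must resolve or return to their pre-illness level. For three of them the rule refers to the baseline grade: "dyspnea, cough or chest pain, which, if persistent, must be at least one grade lower than baseline and no worse than grade 1 (mild").

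Protocol 7.4.2 applies the primary method to the other time-to-event endpoints. Time to resolution of an individual symptom is therefore also analysed without that symptom's baseline grade.

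**The concern.** A patient who enters with many severe symptoms has more to clear than one who enters with two moderate ones. Baseline burden is thus the natural candidate for a strong predictor of this endpoint. In a proportional-hazards setting, omitting a strong predictor pulls the estimated treatment hazard ratio toward 1 and weakens the test.

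Much rests on this one test. Protocol 7.4.3 allows inference on any secondary endpoint, including hospitalization or death, only if the primary succeeds. Protocol 7.1 itself calls the target effect relatively large and allows that the true effect may be smaller.

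**Working it through.** **Inputs from Protocol 7.1.** The design is set "in order to detect a hazard ratio for sustained recovery=1.5 comparing the active group to placebo group with 3:2 allocation ratio" and "to provide 80% power using a log-rank test at a two-sided significance level of 0.05"; "a total of 201 recovery events are required". The active share is 0.6, so the allocation term is 0.6 × 0.4 = 0.24. Control recovery is 80% by day 57, with 250 patients (150 and 100).

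**Step 1: reproduce the plan's figure.** Schoenfeld events = (1.960 + 0.842)² / (0.24 × (ln 1.5)²) = 7.849 / (0.24 × 0.1644) = 198.9, so 199 against the stated 201. Power at 201 events = Φ(√(201 × 0.24) × 0.4055 − 1.960) = Φ(0.856) = 80.4%. Patients: 201 / 0.80 = 251.3 against the stated 250. The figures reproduce, and the calculation contains no covariate term.

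**Step 2: simulate with and without the score.** Assumptions: exponential recovery times, control recovery 80% by day 57, censoring at day 57, and a standard normal baseline score whose log-hazard per SD is b (a higher score means slower recovery). b is not in the documents, so it is varied. There are 2,000 trials per setting, with a Monte Carlo standard error near √(0.8 × 0.2 / 2000) = 0.9 points. Powers are shown unrounded only so that the differences can be checked.

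*HR 1.5 read as the unadjusted effect* (235 patients, about 202 to 204 events; conditional HR set to 1.515, 1.565, 1.625 and 1.70 so that the unadjusted HR is about 1.5):

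| b | Recovery HR per SD, exp(−b) | Log-rank | Cox with score | Gain |
|---|---|---|---|---|
| 0.2 | 0.82 | 79.35% | 81.70% | 2.35 |
| 0.4 | 0.67 | 80.35% | 87.15% | 6.80 |
| 0.6 | 0.55 | 78.90% | 90.95% | 12.05 |
| 0.8 | 0.45 | 79.70% | 95.60% | 15.90 |

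*HR 1.5 read as the effect conditional on the score* (250 patients, about 212 to 217 events):

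| b | Log-rank | Cox with score | Gain |
|---|---|---|---|
| 0 | 83.90% | 83.30% | −0.60 |
| 0.2 | 80.80% | 82.85% | 2.05 |
| 0.4 | 73.95% | 80.95% | 7.00 |
| 0.6 | 65.75% | 80.30% | 14.55 |
| 0.8 | 57.30% | 80.80% | 23.50 |

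At b = 0.4 the mean estimates were 1.50 with the score and 1.44 without it. With a true HR of 1.0, the adjusted test rejected in 5.15% of trials at both b = 0 and b = 0.8, consistent with 5%.

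**Step 3: covariate or extra strata.** Assume 2 × 2 × 2 × 3 = 24 randomization cells (three regions is an assumption, as are the cell proportions), 250 patients and conditional HR 1.5:

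| b | Stratified log-rank | Stratified Cox with score | Log-rank with score tertiles as extra strata |
|---|---|---|---|
| 0 | 78.05% | 77.40% | 62.95% |
| 0.4 | 68.95% | 74.80% | 58.05% |
| 0.8 | 53.25% | 74.70% | 57.50% |

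As a covariate, the score loses almost nothing when it is useless and gains when it is prognostic. As extra strata, it thins the cells and costs 15.10 points at b = 0 and 10.90 at b = 0.4.

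**The case against.** The strongest reply is that this belongs to a document not yet written. The SAP supplied covers part A, where efficacy is descriptive. A part B SAP will follow, and Protocol 7.6 allows the analysis plan to be adjusted after part A. The recovery definition is itself open (14 or 28 days, with alternatives in SAP 20.1.1), and a supportive adjusted Cox model is already planned. This bears on timing, and the score should be fixed together with the final endpoint. It does not remove the point: Protocol 7.4.1 and SAP 4.2 already state the part B primary method, and the supportive model is not the primary test and names no covariate.

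The second reply is that prognostic strength is unproven and the recovery rule does not run one way. That stands. For cough, dyspnea and chest pain, a patient who starts at mild must clear the symptom fully, while one who starts at moderate or severe need only reach mild. Chronic symptoms need only return to their pre-illness level. The rule of two moderate symptoms at entry also trims the low end of the range. A reader might infer that burden drives recovery time by construction; the definition makes that likely but does not establish it.

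Third, a reader might infer that the trial is underpowered, since the log-rank column in the conditional table falls well below 80%. The documents do not support that. They size a log-rank test with no covariate, and nothing says that 1.5 is a conditional effect.

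Fourth, a reader might apply the linear-model rule and say that, at a correlation of 0.5, 201 events act like 201 / (1 − 0.25) = 268. That rule does not carry over to Cox regression, where the gain comes from the estimate moving away from 1. With exponential times, Var(log T) = 1.645 + b². A correlation of 0.5 needs b² / (1.645 + b²) = 0.25, so b = 0.74, a recovery HR of about 0.48 per SD. No figure in the documents supports a predictor that strong.

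Finally, adjustment is not free of cost; the costs are set out with the fix.

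**Conclusion.** The point holds as a missed efficiency that should be taken up while the part B SAP is open. The primary test and hazard ratio adjust for the randomization factors alone and omit a baseline measure that is collected from everyone and probably prognostic. The sample size is not in error: 201 events give about 80% power for an unadjusted hazard ratio of 1.5.

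The gain from adjustment is about 0 points if the score carries no information, about 2 at b = 0.2 and about 7 at b = 0.4. At b = 0.6 to 0.8 it is about 12 to 24, depending on which effect 1.5 describes. These sizes rest on an assumed b, exponential times and a normal score with a linear effect. The documents select no value of b.

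**What to change.** In Protocol 7.4.1 and the part B SAP, before any part B unblinding:

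- Take the primary test and hazard ratio from the Cox model stratified by the randomization factors, combining small strata as SAP 4.2 allows, with treatment and one prespecified baseline diary score as covariates. An example is the sum of the 0–3 grades over the 14 items other than fatigue, smell and taste. State how the diarrhea and vomiting frequency categories map to grades. Do not add the score as strata.
- Keep the stratified log-rank test and Kaplan-Meier curves as supportive.
- Use the same statistic in the interim promising-zone and futility rules, because Protocol 7.4.3 rests type I error control on the final test statistic.
- For time to resolution of each symptom, add that symptom's baseline grade as a covariate.

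Part A can be used to check the form of the score, since it stays outside the part B analysis and may be shared with the sponsor. It cannot measure b well: if 80% of 60 patients recover, there are 48 events and the standard error of b is near 1/√48 = 0.14. The score should therefore not be dropped for lack of significance there.

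The cost is wording in two documents and alignment of the DSMB charter, with no patients or data added. The hazard ratio becomes conditional on the score and relies on a simple functional form, which fits the three respiratory and chest items imperfectly because their threshold is not monotone in baseline grade. Keeping the randomization factors as strata avoids assuming proportional hazards across them.

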7.4.2 Analysis of the secondary efficacy endpoints

Comparison between active treatment and placebo of the following secondary efficacy endpoints will be performed:

- 1) Incidence of hospitalization or death: the primary assessment of this endpoint will be among patients in the high risk group. This has been defined preliminarily above. The group may be redefined and recruitment restricted based on analysis at the end of part A and again in the interim analysis of part B. Additional secondary endpoints include:
- 2) The proportion of patients who are PCR-negative at each time point assessed, days 8, 15, 29 and 57 from the start of treatment (landmark analysis);
- 3) Time to resolution of individual disease-related symptoms present at baseline;
- 4) Development of new disease-related symptoms or pneumonia on study:

5) Changes in laboratory markers of disease severity, i.e., oxygen saturation, CRP, lymphocyte count and D-dimer levels, from baseline to time points at which these are measured on study;

The time frame for all endpoints unless otherwise stated is from Day 1 (day of first dose of study medication) through study Day 57. The time to event endpoints will be analyzed using the methods described for the primary endpoint above.

Binary (Yes/No) endpoints (development of pneumonia, hospitalization and mortality) will be summarized using counts and percentages for each group. A 95% confidence interval will be constructed for each proportion. Population-level risk differences will be used to estimate treatment effect. More specific details will be provided in the SAP.

Changes from baseline in continuous variables will be summarized by descriptive statistics and analyzed using repeated-measures model. Data will be log transformed, as needed.

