#### 1. Introduction

This statistical analysis plan (SAP) expands the summary analysis plan in *Section 7 Data Analysis* and *Statistical Considerations* of the study protocol "Phase 2/3 Study of Upamostat, a Serine Protease Inhibitor, or Placebo for Treatment of COVID-19 Disease" authored by the sponsor (RedHill Biopharma Ltd.) approved amendment 4 version dated June 15, 2021. This is the first version of the SAP and there are no changes to track from a previous version. This SAP is intended for analysis of part A of the study. *The SAP for part B will be finalized after analysis of data from part A and an SAP for analysis of part B of the study generated. Modifications may be made to the analyses planned for part B based on that review as allowed in the approved protocol or based on protocol amendments made after Part A analysis. Based on the current protocol, changes that may be made after Part A analysis are highlighted in bold and italicized throughout this SAP. The SAP for part A will be approved by the sponsor before unblinding of Part A data. Deviations from this SAP will be documented in the part A analysis report. Changes after approval of version 1.0 of the SAP are summarized in the appendix.* 

The scope of analysis provided in this part A SAP includes plans for analysis after all subjects enrolled in Part A complete treatment or discontinue early and complete follow-up. The analysis of part A in this SAP is divided into first and second tier analyses. The first-tier analysis is prioritized to allow to proceed to part B expeditiously. Where procedures and analyses described in the SAP differ from those in the protocol, those in the SAP take precedence.

Study: RHB-107-01 Page 7 of 28

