Binary (Yes/No) endpoints (i.e., development of pneumonia diagnosed clinically, hospitalization and mortality) will be summarized using counts and percentages for each group. A 95% confidence interval will be constructed for each proportion. For endpoints other than mortality, (e.g, development of new

Study: RHB-107-01 Page 21 of 28

disease-related symptom on study), analysis will treat death before the event of interest as the most unfavorable possible outcome for this endpoint. Additional rules for handling missing data will be determined during blind review of the data and documented prior to unblinding.

Changes from baseline in laboratory markers (continuous variables) will be summarized by descriptive statistics. For oxygen saturation, which is measured twice daily throughout the study period, patterns will be presented visually. The median value for each subject from the preceding week will be used (e.g., for the Day 8, the median SpO2 value for Days 2-8 will be used). The daily SpO2 will be the subject's median of the 14 values collected (morning and evening). The morning and evening SpO2 will be the median of the 7 values at that time of day. Descriptive tables will be done for Days 1, 15, 22, 29, 36, 43, 50, 57.

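### The part B marker analysis models change from baseline without naming the baseline value as a covariate; adding it would gain precision at almost no cost

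*Protocol*

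**What the plan says.** Protocol 7.4.2 lists the laboratory markers as the fifth and last secondary efficacy endpoint: "Changes in laboratory markers of disease severity, i.e., oxygen saturation, CRP, lymphocyte count and D-dimer levels, from baseline to time points" at which they are measured. The method is given in two sentences. The first is "Changes from baseline in continuous variables will be summarized by descriptive statistics and analyzed using repeated-measures model". The second is "Data will be log transformed, as needed". No fixed effects, covariates or covariance structure are listed, and there is no rule for when or for which marker the log scale applies.

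SAP 4.2 is the only general covariate rule. It states that "In part B only, primary analyses will adjust for stratification factors used in the randomization", and then that "Additional covariate adjustments may be done in sensitivity and" exploratory analyses. Baseline marker values are not mentioned.

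The SAP supplied covers part A. For these markers, SAP section 13 plans no model: "Changes from baseline in laboratory markers (continuous variables) will be summarized by descriptive statistics". Its introduction says of the later document: "The SAP for part B will be finalized after analysis of data from part A".

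**The concern.** In acute COVID-19 the starting level of a marker such as CRP or D-dimer can differ widely between patients, and a patient who starts high has further to fall. Change is then correlated with the starting value. A change-score model with no baseline term leaves that variation in the error and gives wider intervals than a baseline-adjusted model in the same patients.

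Where the protocol wants adjustment it says so. Section 7.4.1 specifies stratification for the primary endpoint and a supporting Cox model that controls for baseline imbalance. Section 7.4.2 has no counterpart for the markers, and SAP 4.2 read literally makes any further covariate optional and outside the main analysis.

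Precision matters here because Protocol 1.3 treats these markers as early evidence of drug activity and follows CRP only where a central laboratory can standardize it. CRP may therefore be available in fewer than the 250 part B patients. The open log scale is a separate looseness: Protocol 7.4.3 puts the secondary endpoints in a sequential testing order, and an endpoint that may be interpreted inferentially should have its scale settled beforehand.

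**Working it through.** **The plan's own figure.** No figure is given for the markers. The only sizing is for the primary endpoint: "a total of 201 recovery events are required, to provide 80% power using a log-rank test at a two-sided significance level of 0.05" (Protocol 7.1), with hazard ratio 1.5 and 3:2 allocation.
- Schoenfeld events: (1.960 + 0.842)² / (0.6 × 0.4 × (ln 1.5)²) = 199, against 201 stated. Power at 201 events is 80.4%.
- Patients: 201 / 0.80 = 251.25, against 250 stated.

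Both reproduce, and neither depends on the marker model.

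**Inputs for the marker comparison.** Arm sizes of 150 and 100 are from Protocol 7.1. Assumed, because the documents are silent: equal SD s at baseline and follow-up, correlation r between them, one post-baseline visit and complete data.

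**Formulas.** The variance of the treatment difference is proportional to
- 2s²(1 − r) for the change score without baseline;
- s²(1 − r²) with baseline as a covariate.

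The ratio is (1 − r²) / [2(1 − r)] = (1 + r)/2.

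| Assumed r | Variance ratio | Fall in standard error | Power with baseline, for an effect with 80% power without it |
|---|---|---|---|
| 0.3 | 0.65 | 19.4% | 93.5% |
| 0.5 | 0.75 | 13.4% | 89.9% |
| 0.7 | 0.85 | 7.8% | 86.0% |
| 0.9 | 0.95 | 2.5% | 82.0% |

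Worked line at r = 0.5, in SD units: √(1/100 + 1/150) = 0.1291. The unadjusted standard error is √1.0 × 0.1291 = 0.1291, and the effect with 80% power is 2.802 × 0.1291 = 0.362. The adjusted standard error is √0.75 × 0.1291 = 0.1118. Power is then Φ(0.362/0.1118 − 1.960), about 0.90.

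A simulation of 4,000 runs per value, 150 against 100 patients, gave variance ratios of 0.65, 0.77 and 0.87 at r = 0.3, 0.5 and 0.7.

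**Departures from the single-visit, equal-SD case.**
- Average of four post-baseline visits, compound symmetry: the variance is (1 + 3r)/4 + 1 − 2r without baseline and (1 + 3r)/4 − r² with it. The ratios are 0.385/0.875 = 0.44, 0.375/0.625 = 0.60 and 0.285/0.375 = 0.76 at r = 0.3, 0.5 and 0.7.
- SD shrinking as markers normalize, with k the follow-up SD over the baseline SD: the ratio is k²(1 − r²)/(1 + k² − 2rk). At an assumed k = 0.7 it is 0.42, 0.47 and 0.49 for the same r.

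**Carry-over of chance imbalance.** With equal SDs, a baseline difference d between arms shifts the expected change-score difference by −(1 − r)d, which is 70%, 50% and 30% of d at r = 0.3, 0.5 and 0.7. Averaged over randomizations the shift is zero.

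**If baseline is already in the model,** as a covariate or as a constrained response, the gain is essentially zero.

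**The case against.** The strongest reply is that an unspecified model is not a wrong one. Section 7.4.2 does not list treatment or visit either, and nobody would conclude that they are absent. A change-from-baseline outcome is fully compatible with a baseline covariate. The opening of Protocol section 7 describes the analyses as provisional, and the part B SAP, where model terms belong, is still to come. All of this stands. A reader might infer that the plan excludes baseline; the documents do not say so.

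A reader might also infer that chance imbalance passes in full into the treatment estimate. It does not, because subtracting baseline removes part of it and, with equal SDs, a fraction 1 − r remains with opposite sign. Nor is there bias.

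A third inference would be that the trial needs more patients. Part B enrolment is set by recovery events, so a variance ratio for a marker does not bear on it.

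The endpoint is also last in the 7.4.2 list, tested only if the primary and every earlier secondary endpoint succeed, and that order was itself not final. Finally, 7.4.2 does not say that the log scale would be chosen on unblinded data.

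What remains is that no text commits the main marker analysis to baseline adjustment, and the one covariate rule points the other way by default.

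**Conclusion.** The point holds as a low-priority improvement. Followed as written, the part B marker analysis may omit the baseline value from its main model. If it does, estimates remain unbiased but less precise: the single-visit variance ratio is 0.65 to 0.85 over assumed correlations of 0.3 to 0.7, and approaches 1 as the correlation nears 1. The size rests on assumed correlations, equal SDs and complete data, and applies only if baseline is in fact left out. With complete data, adjustment costs no more than a trivial loss of degrees of freedom, so there is no precision argument against it. The open log scale is a direct reading of the text and does not depend on the baseline question. Enrolment, the 201 events and the primary conclusion are untouched.

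**What to change.** In Protocol 7.4.2 and the part B SAP, state that the main repeated-measures model for each listed marker with a baseline measurement contains treatment, visit, treatment-by-visit, baseline value and baseline-by-visit, with baseline on the same scale as the outcome. Treating baseline as a constrained response would also be acceptable if stated in advance. Fix the log scale for skewed markers, for example CRP and D-dimer, before unblinding.

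Two limits apply. Troponin and ferritin appear among the Synopsis objectives but not in the 7.4.2 list, so the sentence covers them only if they are analysed. For lymphocyte count, confirm that a baseline blood count is drawn: the CBC row of Table 1, as it reads in the extracted text, shows no baseline mark, which may be an artefact of extraction.

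The cost is one sentence on the model and a short rule on scale. No new data are needed for markers that already have a baseline measurement.
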